1.4 Clinical Experience with ASLAN003

ASLAN003 has been administered to healthy subjects in 3 Phase I studies.

The safety, tolerability and PKs of ASLAN003 and its metabolites have been evaluated in healthy male subjects following oral administration of single ascending doses of 1, 2, 5, 10, 25, 50 and 100 mg (7 dose levels) of ASLAN003 in healthy male Caucasian subjects in a Phase I study (*Study M/186323/01*). Although $t_{1/2}$ was consistent across the different dose levels, C_{max} and AUC increased less proportionally with increasing dose. The main metabolite circulating in plasma was LAS186558 with mean AUC values across all administered doses between 3.4% and 9.8% of the mean AUC values of the parent drug; metabolite. LAS186876 was a minor metabolite and was formed at less than 2% of parent drug AUC. ASLAN003 was well-tolerated at all doses studied.

In another Phase I, randomized, double-blind, placebo-controlled, 2-part study (*Study ASLAN003-001*), the safety, tolerability and PKs of single ascending doses (SAD) and multiple ascending doses (MAD) of ASLAN003 were evaluated in healthy Asian subjects. ASLAN003 administered as single and multiple doses of 100 mg, 200 mg, and 400 mg under fed and fasted conditions safe and well-tolerated in healthy subjects. For ASLAN003 and its 2 oxidative plasma metabolites, there was no evidence of departures from dose proportionality following a single dose under fasted conditions in terms of area under the curve from time 0 extrapolated to infinite time ($AUC_{(0-inf)}$), whereas the analyses revealed less dose proportional increase in C_{max} .

Following a single oral dose of 200 mg ASLAN003 with a high-fat meal (fed state), the median t_{max} was delayed by 1.5 hours as compared to the 200 mg dose in the fasted state. The C_{max} and AUC of ASLAN003 were increased by 29% and 18% respectively and inter-subject variability was reduced. Mean $t_{1/2}$ was similar under both fed and fasted dosing conditions for both parent drug and the 2 metabolites.

In the MAD part of the study (100 mg, 200 mg, and 400 mg, QD for 7 days), the plasma AUC_{tau} and C_{max} for ASLAN003 and LAS186876 revealed no evidence of departures from dose proportionality with increasing doses of ASLAN003 when taken after a meal. However, the AUC_{tau} and C_{max} for LAS186558 increased in a less dose-proportional manner.

The t_{max} and $t_{1/2}$ for ASLAN003 were dose-independent following QD doses across the selected dose range; 5 and 16 hours, respectively. Steady-state concentrations of ASLAN003, LAS186558, and LAS186876 were achieved by Day 4 across the selected dose range. Following daily repeated dosing, exposure to ASLAN003 and LAS186558 (AUC) appeared to accumulate slightly (less than 30% increase). The exposure was higher in elderly subjects (AUC_{tau}) of ASLAN003 was increased by 53% and C_{max} by 41%), which may be explained by their lower body weight. Renal elimination of free (unconjugated) ASLAN003, LAS186558, and LAS186876 were negligible (<0.8% of the administered dose). Phase II metabolism appeared to be an important route of elimination. Conjugation was most prevalent for ASLAN003 and LAS186558.

Most frequently reported adverse events (AEs) across this ASLAN003-001 study were abnormality in laboratory investigations and included elevated alanine aminotransferase (ALT), aspartate aminotransferase (AST), gamma glutamyltransferase, blood cholesterol increased, blood creatine phosphokinase increased, electrocardiogram (ECG) PR, and blood glucose increased. The safety assessment results reported in patients aged ≥ 55 years were mostly comparable with those of younger subjects other than for greater changes in the laboratory assessments in the elderly subjects compared to the younger subjects, notably the liver function tests.

Another Phase IB study (*Study ASLAN003-002*) evaluated the safety, tolerability and PKs of multiple doses of 100 mg of ASLAN003 QD for 14 days in healthy elderly Asian subjects (age > 55 years old). The study was conducted at a single center in Singapore where 7 of the planned 8 elderly subjects were enrolled into Stage 1 of the study, of which

5 subjects received ASLAN 100 mg QD on Day 1; and 4 of these subjects received ASLAN 100 mg QD on Day 8. Only 1 subject completed 14 days of QD dosing. Stage 2 of the study was not conducted. Following daily repeated dosing, mean plasma exposure to ASLAN003 expressed as $AUC_{(0-24)}$ increased 1.2-fold after multiple dosing on Day 8 compared to a single dose on Day 1. Following repeat QD dosing, the relative systemic exposures to the metabolites LAS186558 and LAS186876 were around 10% and 1%, respectively.

Elevations in liver function tests in ASLAN003-002 study was similar to the observation in the previous study (ASLAN003-001). This is likely to be a class effect of DHODH inhibitors. Monitoring of liver function in patients is recommended. It is possible that elderly subjects could be more susceptible to these effects.

1.5 Known or Potential Risks Associated with ASLAN003

ASLAN003 has demonstrated an acceptable safety profile in nonclinical toxicology studies and completed Phase I studies in humans. However, as with any new investigational drug, unexpected AEs may occur with the use of ASLAN003. The following is a summary of potential risks; additional details are presented in the IB:

- ASLAN003 must not be administered to pregnant or nursing women.
- ALT, AST, and total bilirubin along with signs or symptoms of liver toxicity should be monitored during ASLAN003 treatment.

1.6 Rationale for the Study

A recent publication by Sykes et al. (2016)¹⁴ summarized 5 years of primary science and identified DHODH as a critical enzyme in the differentiation of human AML blast cells to granulocytes. *In vitro* studies with ASLAN003 have demonstrated that the compound induces the differentiation of AML cell lines: KG-1, MOLM-14 and THP-1, through inhibition of DHODH. *Ex vivo* analyses with ASLAN003 have also demonstrated myeloid differentiation of primary AML blast cells obtained from patients.

In Phase I studies, ASLAN003 was generally well-tolerated. No clinically significant changes in liver transaminase enzymes were noted in healthy male volunteers (except for elderly subjects who had greater liver function alterations) when ASLAN003 was dosed at clinically relevant exposures. ASLAN003 may offer an important addition to induction therapies, or in combination with other therapies such as azacytidine, or as a monotherapy.

We now intend to study the effects of ASLAN003 over a dose range, with the purpose to a) study efficacy in AML patients, and b) determine the dose optimum dose based on the combined efficacy and safety data.

ASLAN003 is very potent in inducing differentiation of AML cells lines ($ED_{90} < 50$ nM for THP-1). From these predictions, a starting dose of 100 mg QD would be most appropriate to obtain a good coverage of ED_{90} values. Since ASLAN003 is an acidic compound, the protein binding effect in human plasma should be considered. A starting

dose of ASLAN003 100 mg should obtain full 24-hour coverage of the effect. The fact that blast cell counts vary drastically among AML patients, suggests that a higher treatment dose might be necessary to show the optimum efficacy in some patients. Considering that AML patients are generally older in age and often carry comorbidities, it may be prudent to use doses lower than the maximum dose (400 mg) employed in healthy subjects. Therefore, the study will use 3-4 dose groups: 100 mg QD, 200 mg QD, 100 mg BID and potentially an additional cohort of 200 mg BID, which may only commence, subject to agreement from the steering committee based on a review of safety data from the 100 mg BID cohort. .

According to the pharmacokinetic data from the patients who had been treated with ASLAN003 100mg once daily in this study, the trough plasma concentration is below the IC50 of enzymatic hDHODH. A simulation model shows increasing the frequency of ASLAN003 administration keeps the plasma concentration of ASLAN003 above the IC50. Therefore, the dose and dosing frequency in two cohort (ASLAN003 100 mg BID and ASLAN003 200 mg BID) are changed and one additional cohorts with dosing ASLAN003 twice daily is added to the study design. The daily total dose of ASLAN003 is still within the maximum dose, tested safe in prior trials.

2 STUDY OBJECTIVES

2.1 Primary Objective

Part 1:

- To determine the optimum dose of ASLAN003 monotherapy based on the efficacy, safety and tolerability profile in AML patients who are ineligible for standard therapy.

Part 2:

- To provide a preliminary estimate of the efficacy of ASLAN003 at the optimum dose selected from Part 1.

2.2 Secondary Objective

Part 1:

- To evaluate the PKs of ASLAN003 and its metabolite LAS186558 in patients with AML.

Part 2:

- To further assess the safety and tolerability data of ASLAN003 at the optimum dose selected from Part 1.

2.3 Exploratory Objectives

- To examine the myeloid differentiation effects of ASLAN003 using assays including but not limited to an *ex vivo* flow cytometry assay.
- To explore possible relationships between molecular abnormalities and measures of clinical response in patients with AML.

3 OVERALL DESIGN AND PLAN OF THE STUDY

3.1 Study Design Overview

This is a multicenter, single arm, non-randomized, Phase IIA Study to evaluate ASLAN003 as a monotherapy in patients with AML.

AML patients who are ineligible for standard treatment including, but not limited to the following conditions, will be enrolled in the study:

- Newly diagnosed patients who are ineligible for standard therapy i.e., standard dose induction chemotherapy and reduced dose chemotherapy;
- Patients with relapse from prior remission;
- Patients with failed response to prior therapy including chemotherapy, hypomethylating agents, and bone marrow transplantation.

Rationale for dose selection: ASLAN003 is very potent at inducing differentiation in AML cells lines ($ED_{90} < 50$ nM for THP-1). From these predictions, a starting dose of 100 mg QD would be the most appropriate to obtain a good coverage of ED_{90} values. Since ASLAN003 is an acidic compound, the protein binding effect in human plasma will be high leading to lower levels of free drug, a starting dose of 100 mg QD is recommended to provide full 24-hour coverage.

Blast cell counts vary widely among AML patients, which may indicate that a higher treatment dose of ASLAN003 might be necessary to obtain the optimum efficacy. However, it is also important to consider the age and fitness of the AML patients who might have multiple comorbidities, and the maximum experienced dose (400 mg QD) established in healthy subjects might not be tolerated. Considering that AML patients are generally older in age and often carry comorbidities, it may be prudent to use doses lower than the maximum dose (400 mg) determined in healthy subjects.

Up to a total of 18-24 patients will be enrolled in Part 1 of this study - 6 patients in each dose cohort. The planned sequence of cohort enrollment is ASLAN003 100 mg QD, 200 mg QD, 100 mg BID and potentially an additional cohort of 200 mg BID (this additional cohort of 6 patients may commence, subject to agreement by the steering committee (SC) based on a review of safety data in 100 mg BID cohort).

A SC meeting will be set up to review all the clinical information including efficacy, safety, and PK data. Details of the SC outcome will be specified in the SC charter.

An expansion cohort of 20 patients (Part 2) will be recruited to study the optimum dose selected by the SC. The optimum dose will be selected from at least one cohort showing tolerable safety profile and clinical benefit in disease presentation. Details will be specified in the SC charter.

Patients with especially high blast cell count should be closely monitored for a possible differentiation syndrome. Investigators could manage suspected patients proactively

according to the recommendation in the National Comprehensive Cancer Network (NCCN) guidelines APL differentiation syndrome section.

Bone marrow aspiration samples will be collected before the first day of treatment, will be cultured *in vitro* and incubated with ASLAN003 to examine the myeloid differentiation efficacy of ASLAN003 *ex vivo*. Molecular studies will also be done to check for any phenotypic and genotypic changes in the patients' bone marrow sample. A bone marrow aspiration smear will be processed locally. *Ex vivo* assay and molecular assessment will be processed centrally (Please refer to the lab manual for details).

[figure not shown]
All patients will continue to receive ASLAN003 until disease relapse, treatment failure, unacceptable toxicity, withdrawal of consent or death.

For the PK evaluations, blood samples will be collected at the following timepoints on Day 1 and Day 8 of the QD, 28-day treatment cycle: pre-dose, 1, 2, 4, 5, 6, 8, and 24 hours post dose. In BID regime i.e 100mg BID and 200mg BID the PK sampling will be done at following timepoints: pre-dose, 1, 2, 4, 5, 6, 8, and 12 hours (or evening pre-dose).

For Part 2 PK evaluations- Steering Committee will decide whether PK analysis is required or not and ASLAN pharmaceuticals will be updated accordingly

The schedule of the assessments are presented in Table 1.

Figure 1: Study Design Description

Abbreviations: AML = acute myeloid leukemia; QD = once daily, BID = twice daily.

3.2 Steering Committee

A Steering Committee (SC) will be established for the purpose of assessing the efficacy, safety, tolerability, and PK data for the duration of the study.

The SC will evaluate the progress of the study on an ongoing basis and will make key decisions on the study in the best interest of the patients. Examples include continuation or discontinuation of the study, investigation of a lower dose level not stated in the protocol if efficacy is observed at a higher dose level. Details of the steering committee outcome will be specified in the SC charter.

An expansion cohort of 20 patients (Part 2) will be recruited to study the optimum dose selected by the SC. The optimum dose will be selected from at least one cohort showing tolerable safety profile and clinical benefit in disease presentation. Details will be specified in the SC charter.

3.3 Criteria for Evaluation of the Study

3.3.1 Primary Endpoints

Part 1:

The primary objective of determining the optimum monotherapy dose of ASLAN003 in AML patients is based on the following endpoints:

- **Overall Complete Remission Rate (OCRR):** Defined as the proportion of patients with a best response of complete remission (CR) or complete remission with incomplete hematologic recovery (CRi), defined in accordance with the International Working Group (IWG) Response Criteria in AML.
- **Safety and tolerability:** Based on AEs, safety assessments (including vital signs, ECG parameters, clinical laboratory tests) and treatment exposure/dose intensity.

Part 2:

- **OCRR:** defined as described above for *Part 1*.

3.3.2 Secondary Endpoints:

- Efficacy (*Parts 1 and 2*):
 - **Relapse Free Survival (RFS):** Defined as the time the criteria for remission (CR or CRi) are first met until there is evidence of patient relapse, regardless of whether the patient is still taking study drug. Relapse is defined as:
 - The reappearance of leukemic blasts in the peripheral blood or > 5% blasts in the bone marrow not attributable to any other cause;
 - The appearance of new dysplastic changes;
 - The reappearance of or development of cytologically proven extramedullary disease;
 - The reappearance of a cytogenetic or molecular abnormality.

- **Clinical Benefit Rate (CBR):** defined as the proportion of patients with an AML IWG best response of CR, CRi or partial remission (PR).
- % change from baseline in BM blasts at Day 29.
- Safety and tolerability (**Part 2 ONLY**):
 - Based on AEs, safety assessments (including vital signs, electrocardiogram [ECG] parameters, clinical laboratory tests) and treatment exposure/dose intensity.
- Pharmacokinetics (Part 1 ONLY):

If estimable, the following parameters will be calculated on Days 1 and 8, Cycle 1:

- PK parameters for ASLAN003: maximum observed plasma concentration (C_{max}), C_{max} at steady state ($C_{max ss}$), trough plasma concentration (C_{trough}), time corresponding to occurrence of C_{max} (t_{max}), and $C_{max ss}$ ($t_{max ss}$), AUC over the dosing interval (AUC_{tau}), AUC_{tau} at steady state ($AUC_{tau ss}$), terminal elimination half-life at steady state ($t_{1/2}$), effective elimination half-life at steady state ($t_{1/2 eff}$), apparent total clearance of the drug from plasma after oral administration (CL/F), apparent volume of distribution at steady state after oral administration (V_{ss}/F), accumulation ratio for AUC ($RacAUC$), and accumulation ratio for C_{max} ($RacC_{max}$).
- PK parameters for LAS186558: C_{max} , C_{trough} , t_{max} , AUC_{tau} , $t_{1/2 eff}$, $RacAUC$, $RacC_{max}$, metabolic ratio (MR) for C_{max} (MRC_{max}) and AUC (MRAUC).

3.3.3 Exploratory Endpoint (Parts 1 and 2):

- Assessment of the degree of blast cell differentiation by ASLAN003 using assays including but not limited to *ex vivo* flow cytometry assay using selected myeloid cell markers (such as CD11b).
- Assessment of the molecular abnormalities of AML blast cells at baseline.

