3.4 Duration of the study participation

The study duration consists of the following periods:

Screening Period: 28 days

Treatment Period: All patients will receive a continuous 28-day treatment cycle of ASLAN003 until disease relapse, treatment failure (defined as failure to achieve a PR or higher within 4 cycles) unacceptable toxicity, withdrawal of consent or death.

Follow-up Period: All patients will be required to complete a safety follow-up visit within 28 days after the last dose of study treatment. All patients achieving CR or CRi will be followed for survival every 12 weeks post end of treatment (EOT) until disease relapse or death (in the absence of disease relapse) to find out the RFS.

Visit Schedule: In order to address the primary objectives of the study, if treatment is interrupted for any reason, it is important that all planned safety and efficacy assessments are performed at the scheduled time, regardless of whether the patient is receiving study treatment, or not, at the time.

The planned duration of entire study (treatment and follow-up) is approximately 2 years.

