Failure to meet the criteria for CR, CRi or PR after 4 cycles of treatment will result in a best response of treatment failure.

For the evaluation of OCRR, a binary variable will be created to indicate complete response status of each patient (complete responder or non-responder) defined as follows:

A patient will be classified as a complete responder if either of the following are achieved during the study:

- Achievement of CR
- Achievement of CRi

Patients who do not satisfy the CR criteria outlined above (including patients with PR, treatment failure and any patients without evaluable post-treatment assessments) will be classified as non-responders for the assessment of OCRR.

Best response status will also be assessed. A patient's best response is defined as the best AML visit response observed, ranked in the following order:

CR > CRi > PR > Treatment failure.

Based on the above definitions, the following efficacy endpoints will be evaluated:

Overall Complete Remission Rate: Defined as the proportion of patients with a best response of CR or CRi, defined in accordance with the IWG Response Criteria in AML, and described above.

Relapse Free Survival: Defined as the time the criteria for remission (CR or CRi) are first met until there is evidence of patient relapse or death from any cause (whichever happens first), regardless of whether the patient is still taking study drug.

Relapse is defined as:

- The reappearance of leukemic blasts in the peripheral blood or > 5% blasts in the BM not attributable to any other cause
- The appearance of new dysplastic changes
- The reappearance of or development of cytologically proven extramedullary disease
- The reappearance of a cytogenetic or molecular abnormality

Clinical Benefit Rate: Defined as the proportion of patients with an AML IWG best response of CR, CRi or PR.

The percentage change from baseline in BM blasts and peripheral blood blasts at Day 29 will also be evaluated.

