8.2 Sample size determination

This Phase IIA study is not formally powered. For Part 1, the proposed design of up to 6 patients per dose cohort has been selected to provide an assessment of the safety, tolerability and efficacy of up to 4 dose cohorts of ASLAN003, in order to select the most appropriate dose for further exploration in Part 2.

Part 2 is not formally powered. The sample size of 20 patients has been selected to provide further efficacy and tolerability data at the selected dose level from Part 1, prior to conducting larger randomized trials in AML.

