3.1.2 Relapse-Free Survival

Relapse-free survival (RFS) is a secondary endpoint in Parts 1 and 2 and is defined for the sub-group of patients classified as responders for OCRR.

RFS is defined as the time the criteria for remission (CR or CRi) are first met until there is evidence of patient relapse, regardless of whether the patient is still taking study drug or has started other anti-AML treatment prior to relapse. (Note, the onset of the CR/CRi must have been before the start of subsequent anti-AML treatment to be classified as a responder for OCRR). Relapse is defined as:

- The reappearance of leukemic blasts in the peripheral blood or >5% blasts in the bone marrow not attributable to any other cause
- The appearance of new dysplastic changes
- The reappearance of or development of cytologically proven extramedullary disease
- The reappearance of a cytogenetic or molecular abnormality
- Death by any cause

In the event that the blood and bone marrow response assessments for a visit are performed on different dates, RFS will be calculated using the earliest date at which a relapse was detected. For example, if both the peripheral blood and bone marrow were assessed and both found to be indicative of relapse, RFS will use the earlier of the two assessment dates. However, if both were assessed, but only the marrow was found to be indicative of relapse, the date of the marrow assessment would be used as the date of relapse.

As described above, patients who die without evidence of relapse will be considered to have relapsed at the date of death, provided that the death does not occur following two or more missed assessments (up to 56 days following previous assessment). If the death occurs more than 56 days following the previous response assessment, the patient will be censored for RFS at the date of the last efficacy assessment in which they were alive and relapse-free.

Similarly, patients who are determined to have met the criteria for relapse more than 56 days after the last efficacy assessment will also be censored for RFS at the date of the last efficacy assessment in which they relapse-free.

For the purpose of evaluating whether RFS should be censored due to missed visits, a patient will be considered to have missed two assessments if neither the peripheral blood or bone marrow have been assessed for >56 days.

In all study parts, the primary analysis of RFS will be assessed based on the EFR set with a sensitivity analysis based on the FAS.

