7.2 Relapse-Free Survival

RFS will be listed for both study parts. For Part 2 only, if there are sufficient events, RFS will be summarized by using the Kaplan-Meier estimates to present 25th, 50th (median), and 75th percentiles, as well as the number and percentage of events and censored observations.

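### Relapse-free survival treats a death in remission in three ways: the synopsis and Protocol 3.3.2 omit it, Protocol 6.2 always counts it, and SAP 3.1.2 counts it only within 56 days of the previous assessment

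*Protocol*

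**What the plan says.** Protocol 3.3.2, and the synopsis in the same words, start RFS when the criteria for CR or CRi "are first met until there is evidence of patient relapse, regardless of whether the patient is still taking study drug". Four relapse criteria follow: blasts, new dysplasia, extramedullary disease, and a cytogenetic or molecular abnormality. Death is not among them, and neither place gives a censoring rule.

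Protocol 6.2 runs RFS "until there is evidence of patient relapse or death from any cause (whichever happens first"), with no time limit on the death.

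SAP 3.1.2 opens with the relapse-only sentence but adds a fifth item to the relapse list, "Death by any cause". It then says that "patients who die without evidence of relapse will be considered to have relapsed at the date of death", subject to a limit: "If the death occurs more than 56 days following the previous response assessment, the patient will be censored for RFS" at the last assessment at which the patient was alive and relapse-free.

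Protocol 3.4 follows responders every 12 weeks after end of treatment (EOT) "until disease relapse or death (in the absence of disease relapse) to find out the RFS".

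On analysis, SAP 7.2 lists RFS for both parts and adds: "For Part 2 only, if there are sufficient events, RFS will be summarized by using the Kaplan-Meier estimates".

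**The concern.** The protocol defines one secondary endpoint in two ways, and the SAP adds a third. The incomplete definition is the one in the protocol's endpoint section. A patient who dies in remission can no longer relapse. If the 3.3.2 wording were followed, that death would not be an event. By inference it would be censored in the Kaplan-Meier analysis, which would then estimate time to relapse under the name of a survival endpoint.

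Such deaths are plausible. The patients are ineligible for standard treatment, and Protocol 1.6 describes AML patients as generally older and often with comorbidities. Few patients will contribute to RFS, because it is defined only for those who reach CR or CRi, and Part 2 has 20 patients in all. With so few, the handling of one or two deaths can change the event count, the censoring count and the median.

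**Working it through.** The documents give no event count, expected remission rate or RFS assumption, so there is no planned figure to reproduce. The check is a comparison of the texts, followed by illustrations on assumed inputs.

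**1. The definitions side by side**

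| Place | Death in remission, up to 56 days after the previous assessment | Death in remission, more than 56 days after it |
|---|---|---|
| Synopsis; Protocol 3.3.2 | not an event (censored, by inference) | not an event (censored, by inference) |
| Protocol 6.2 | event | event |
| SAP 3.1.2 | event at date of death | censored at last relapse-free assessment |

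The first row disagrees with 6.2 in both columns. The SAP agrees with 6.2 in the first column only.

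**2. How the 56-day limit meets the follow-up schedule**

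SAP 3.1.2 presents 56 days as two missed assessments, and an assessment of either blood or marrow resets the clock. On treatment this fits: haematology is due on Day 1 of each 28-day cycle, and 2 x 28 = 56. After EOT it does not. Contact is every 12 weeks, 84 days, or 77 to 91 with the 7-day window, by telephone or clinic visit (Protocol 7.2.5). The survival follow-up column of Table 1 has no haematology or marrow. A patient can miss nothing and still pass 56 days.

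- If no blood or marrow is taken after the EOT visit, every death in remission more than 56 days after that visit's blood count is an event under 6.2 and censored under the SAP.
- If blood or marrow were taken at every 12-week contact and deaths were spread evenly over the interval (both assumptions), the share of deaths that the SAP counts would be 56/84 = 67% (56/91 = 62% to 56/77 = 73%). The rest would be censored.

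The SAP applies the same limit to relapses, so a relapse found at a 12-week contact with no assessment in between would also be censored.

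**3. Size when all deaths are censored (3.3.2 by inference, against 6.2)**

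Assume constant hazards and let f be the share of first events that are deaths in remission. With relapse hazard h, the death hazard is h x f/(1-f) and the total is h/(1-f). The median is ln2/h with deaths censored and (1-f) x ln2/h with deaths as events. The ratio is 1/(1-f):

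- f = 10%: 1/0.90 = 1.11
- f = 25%: 1/0.75 = 1.33
- f = 50%: 1/0.50 = 2.0

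**4. What two deaths can do among six responders (invented data)**

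Times are 2, 3, 5, 6, 8 and 10, with relapses at 2 and 6, deaths at 3 and 5, and censoring at 8 and 10.

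- Deaths as events: 5/6 = 0.833 at 2; x 4/5 = 0.667 at 3; x 3/4 = 0.500 at 5; x 2/3 = 0.333 at 6. The median is 5.
- Deaths censored: 5/6 = 0.833 at 2; then three remain at risk at 6, and 0.833 x 2/3 = 0.556. The median is not reached.

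**The case against.** The strongest reply is that the operative text largely settles the matter. Protocol 6.2 gives the efficacy definitions and includes death. Protocol 8 leaves analysis detail to the SAP, and the SAP lists death. Responders are followed to relapse or death expressly to obtain RFS. No planned analysis uses a relapse-only rule, so the synopsis and 3.3.2 are incomplete summaries. RFS is secondary and the study is not formally powered. Deaths, survival status and RFS are each listed by patient (SAP 9.2), so the handling can be traced.

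Most of this stands, and it limits the consequence. A reader might infer from 3.3.2 that the planned Kaplan-Meier analysis censors every death in remission and overstates RFS by the ratios above. The documents do not support that: 3.3.2 has no censoring rule, and the SAP counts deaths up to 56 days. A reader might also infer that remission would look more durable the more patients die in it. Under the constant-hazard model the median with deaths censored does not change with f; only the median that counts deaths falls.

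The reply does not dispose of the 56-day limit. There the SAP and 6.2 give different results for the same patient, and the operative text is itself the source of the conflict. Protocol 4.3 does ask sites to continue efficacy assessments in responders until recurrence, so some blood or marrow results may exist after EOT. But it sets no interval, Table 1 schedules none, and a 12-week interval would still exceed 56 days.

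**Conclusion.** The inconsistency is real and in current text. The synopsis and 3.3.2 are wrong as written against 6.2 and the stated purpose of follow-up. SAP 3.1.2 agrees with 6.2 that death counts, but not for deaths more than 56 days after the previous assessment. A reader might suppose that correcting the synopsis and 3.3.2 would be enough; it would not, because the 56-day rule would remain.

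The effect is limited. The primary endpoints are untouched. RFS is only listed in Part 1 and is summarised by Kaplan-Meier in Part 2 only if there are sufficient events. No size can be drawn from the documents, since they give neither the share of deaths in remission nor the number of responders. The factor 1/(1-f) assumes constant hazards, an assumed f and censoring of every death, so it compares the 3.3.2 wording with 6.2 and is not an error in a planned output.

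**What to change.** 1. Replace the relapse-only sentence in the synopsis, in Protocol 3.3.2 and at the start of SAP 3.1.2 with the 6.2 wording, "until there is evidence of patient relapse or death from any cause (whichever happens first").
2. Reconcile the 56-day rule in SAP 3.1.2 with Protocol 6.2 and the 12-week interval, so that all places count the same deaths. One way is to count every death without relapse at its date and keep the gap rule for a sensitivity analysis. Another is to write a gap rule into 6.2 as well, with a limit longer than the scheduled interval. State whether the same rule covers relapses found after a gap.
3. Beside the RFS summary (SAP Tables 14.2.2.1 and 14.2.2.2), show relapses and deaths without relapse as separate counts.

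The cost is a wording edit in three places, one reconciled rule and one added table row. Reported RFS may be shorter than under the 3.3.2 wording.
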